
mini-vaccination stations in communities highly impacted by the pandemic and identifying individual and structural barriers to COVID-19 immunization (Phase 2). Specific aims include:

Aim 1. To evaluate the preliminary impact of 2VIDA! compared to the standard-of-care for COVID-19 vaccination services among Latinx and AA adults ≥ 16 years (N=1000) in San Diego. We will use a 2-armed randomized controlled trial (RCT)* where Latinx and AA adults ≥ 16 years or older from six participating community health centers (CHC) and surrounding communities will be assigned to the 2VIDA! intervention (n=3 CHC; N=500 participants) or to the control site (e.g., standard of care) (n=3 CHC; N=500 participants). Data will be collected on a) sociodemographic characteristics; b) characteristics associated with social marginalization; c) access to and utilization of health care; d) vaccination history, interest, hesitancy and uptake; e) perceptions of the COVID-19 vaccine (e.g., fears, myths, etc.); f) general health; and h) trust in government, research, and social agencies, i) satisfaction with 2VIDA!; at baseline and 4-week follow-up. We hypothesize that at follow-up, compared to control participants, 2VIDA! participants will:

H.1. have increased knowledge about the COVID-19 vaccine (including medically accurate information, benefits, and risks);
H.2. more likely to receive the COVID-19 vaccine;
H.3. more likely to complete vaccine series (based on Centers for Disease Control and Prevention [CDC] recommendations).¹

Aim 2. To assess feasibility, acceptability, and intervention effects of 2VIDA! To assess feasibility and acceptability, we will utilize quantitative methods to track recruitment, condition assignment, participant retention, intervention implementation, and potential threats (e.g., contamination). We will also utilize qualitative methods to assess acceptability via focus groups with participants to understand potential for broad implementation (e.g., what components did they receive of the intervention, client satisfaction, linkage to COVID-19 services). To assess intervention effects, we will examine participant vaccination rates/completion across both groups.

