PHASE II. To evaluate the preliminary impact of 2VIDA! compared to the standard-of-care for COVID-19 vaccination services among Latinx and AA adults >16 years (N=1000) in San Diego. During Phase 2 we will offer the COVID-19 vaccine at the participating SYH community health centers and mini-vaccination stations that will be set-up in these communities (only intervention sites) as part of the intervention efforts (i.e., research activities) to increase access and uptake of the COVID-19 vaccine. We have identified various open spaces (e.g., public parks) in these communities to set-up the vaccination stations. SYH is currently offering the vaccine in their facilities as part of their standard of care. It is available to everyone who is eligible according to the state guidelines and does not depend on participating in this study. However, as part of 2VIDA! we will add these mini-vaccination stations to increase access to the vaccine (e.g., open after 5:00pm and on the weekends). Furthermore, data will be collected to assess individual, social, and contextual factors related to access, acceptance, and uptake of the COVID-19 vaccine including: a) sociodemographic characteristics; b) characteristics associated with social marginalization (e.g., homelessness, food insecurity); c) access to and utilization of health care; d) vaccination history, interest, hesitancy and uptake; e) perceptions of the COVID-19 vaccine (e.g., fears, myths, etc.); f) general health; and h) trust in government, research, and social agencies; i) satisfaction with 2VIDA! at baseline and 4-week follow-up. The survey will last approximately 20 minutes and will be self-administered in both English and Spanish. Following the survey participants will be offered the COVID-19 vaccine and the SYH staff will help them set-up an online appointment onsite for the 2nd dose (1 month follow-up) and will be asked to complete a 5 min survey during the follow-up visit. SYH has trained medical staff and a strict protocol for the storage, handling, and application of the vaccine. UCSD staff will not be involved in this process. Furthermore, participants will be asked to provide separate written consent in order to receive the vaccine that will be conducted by SYH staff. Additionally, two focus groups (FGs) will be conducted with members of Latinx and AA communities (n=8-10 participants per group) to obtain feedback on implementation and ways to improve future sustainability and scalability for future vaccination efforts among vulnerable underserved communities. FGs will be transcribed and reviewed for themes specific to 2VIDA! including personal and structural barriers to medical accurate information and the COVID-19 vaccine, benefits, challenges, feasibility, and scalability.

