
Mini-vaccination stations. We will set-up mini-vaccination stations in the parking of three public parks in the selected intervention sites to support the SYH community health centers. We will set-up signs with the *2VIDA!* project for participants to identify (e.g., same logo and illustrations used during Phase 1) and tent-lined lanes for eligible recipients to drive up. Research assistants will confirm eligibility with potential study participants via verbal assessment of the following inclusion criteria: 1) age 16 years or older; 2) identify as Latinx and/or AA; 3) biologically male or female; 4) be a resident of one of the three communities selected for the intervention (National City, Lincoln Park, Logan Heights, Valencia Park, San Ysidro); 5) literate in English or Spanish; 6) no known history of severe allergic reactions to any components of the vaccine; 7) no history of immune disease; 8) not be pregnant; 9) no plans to move from the area in the following 30 days; 10) able to provide voluntary informed consent; and 11) able to provide complete contact information for themselves (email and phone number) and two additional contact individuals for follow-up. Inside their car they will complete the 10-15 min. survey, receive the COVID-19 vaccine, and pull aside for a 15-minute observation period. We will also set-up additional tents with portable chairs at least 6 feet apart for participants who do not own a vehicle and want to receive the vaccine at the mini-stations. The stations will be opened Monday-Sunday from 7:00am-7:00pm based on the recommendations from our community partners (e.g., some individuals work early/late shifts). We will have two options for the vaccine – a one shot or a two-shot vaccine and the participants will select what type of vaccine they prefer. The vaccines will be available on a first come first-serve basis. For individuals who select a two-shot vaccine, the study staff will schedule the appointment for the participants on site when they receive the 1st dose of the vaccine (as they are waiting during observation period) and give them the date (confirmation). We will use the NextGen program to schedule the follow-up appointments for these participants. For participants who select a one-shot vaccine, they will be reminded that they will receive a text message and/or a link via email (based on their preference) to complete a follow-up survey in 4-weeks. Participants who select a two-shot vaccine will be asked to complete the follow-up survey (4-weeks) when they return for their second shot (during the observation period). We have noticed that percentage of our population has low digital literacy levels and/or limited access to internet or digital technologies which has made enrollment and follow-up challenging. In order to address these barriers, we are proposing to utilize Computer Assisted Telephone Interviewing (CATI)²⁰ and videoconferencing and screen sharing (VCSS).²¹ Both tools have been successfully used for many years in public health as well as by our community partner (SYH) on other similar federal-funded research projects. During enrollment, we would provide the participants with the option to complete the follow-up survey utilizing CATI or VCSS if they require assistance or have limited access to digital technologies. If they chose CATI or VCSS, following the completion of the follow-up survey we would send the incentive via a unique link similar to the follow-up for other participants. The entire team has been trained on these two platforms and would only be used for follow-up. Additionally, SYH will create a temporary patient ID for them and enter them in the system to schedule their second appointment. This is the software program that SYH is currently utilizing to follow-up for vaccine appointments. We believe that utilizing SYH existing infrastructure will allow sustainability and scalability of *2VIDA!*! The participants who select a two-shot vaccine will receive an email or automated

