
text reminder (based on their preference) 24 hours before their scheduled appointment for the 2nd dose. If a participant does not show-up to their appointment for the 2nd dose, we will contact the references that they provided (2 contacts) and reschedule their appointment. This is not an activity routinely done for COVID-19 vaccination efforts by SYH. This is only for *2VIDA!* participants and these tracking mechanisms have been effective in reducing attrition rates in our previous research efforts working with similar populations. Lastly, having participants scheduled for 2nd dosage will allow us to know how many vaccines we need to have available per day following the initial roll-out and avoid any shortages and/or unused dosages. We will follow the same process as with the first dosage, participants will drive up to the tent-lined lanes and inside their car or in tents and chairs (if they come by foot) they will complete the 5 min. survey, receive the 2nd shot of the COVID-19 vaccine, and pull aside for a 15-minute observation period.

The overall goal of this study is to provide medically accurate information and resources on COVID-19 and barriers to accessing the COVID-19 vaccine to increase acceptance, uptake and series completion among predominantly Latinx and African American communities that have been severely impacted by the pandemic. Therefore, individuals who do not meet the eligibility criteria to participate in this research project but are interested in receiving the COVID-19 vaccine will have access to receive the vaccine (just the same as study participants) at the mini-vaccination station or at the participating SYH community health center. We will also follow the same scheduling procedure for non-eligible participants. During the observation period after receiving the vaccine (15 minutes) SYH staff will schedule their appointment for the 2nd dose using the NexGen program at the mini-vaccination station or the SYH community health center that is most convenient for them. This will enable us to provide the ineligible individuals access to the vaccine and have sufficient amounts of the 2nd dose. We will follow the same process for an individual who received the 1st dosage of the vaccine at one of the control sites is seeking to receive the 2nd dosage of the vaccine at the intervention site or mini-vaccination station for non-research purposes.

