However, parental consent will be requested by our community partners (SYH) before they apply the vaccine. Furthermore, participants who refer low digital literacy levels and/or limited access to internet or digital technologies will be informed about the option to conduct the follow-up survey via Computer Assisted Telephone Interviewing (CATI) or videoconferencing and screen sharing (VCSS). Those agreeing to participate will be escorted to a private room within the participating SYH community centers or in their cars or tents (if they come by foot) at the mini-vaccination stations and will provide informed digital consent (e.g., tablet) and complete the survey via a tablet (self-administered). We will set-up mini-vaccination stations in the parking of three public parks in the selected intervention sites and tent-lined lanes for eligible recipients to drive up. Participants will be inside their car and wearing a mask at all times during the consent process. Inside their car they will complete the 10-15 min. survey, receive the COVID-19 vaccine, and pull aside for a 15-minute observation period. We will also set-up additional tents with portable chairs at least 6 feet apart for participants who do not own a vehicle and want to receive the vaccine at the mini-stations. Although the mini-vaccinations will be in open public spaces (e.g., local park) because the set-up between the vaccine stations will be at least 6 feet apart, we expect this will allow for privacy for those that come by foot or do not own a vehicle. However, those participants who feel uncomfortable will be invited to the health center to complete the consent process and survey in a private room. All participants will be assigned a unique identifier to link initial survey and follow-up survey (when they receive the 2nd dose). The baseline survey will take approximately 20 minutes and the follow-up survey last 10 minutes, both will be self-administered (tablet). The research staff will be available in case the participants don't understand a question or need help with any aspect of the survey. Following survey completion, participants will be eligible to receive the COVID-19 vaccine if they provided written informed consent. Although participants would have already been screened for eligibility, the research assistants will confirm again that they do not have any known history of severe allergic reactions to any components of the vaccine, no history of immune disease, and not be pregnant. Further, SYH staff will have parents to provide consent for their children (16–17-year-old) to receive the vaccine. Registered nurses from SYH will proceed to apply the COVID-19 vaccine and as previously mentioned, will observe the participant has no reaction for 15 minutes. SYH will follow strict vaccination protocols (based on the U.S. Food and Drug Administration⁷ and Centers for Disease Control and Prevention recommendations and guidelines)¹ and will report all vaccine administration errors, all serious adverse events, cases of Multisystem Inflammatory Syndrome (MIS), and cases of COVID-19 that result in hospitalization or death following administration of the COVID-19 Vaccine to the IRB and to the Vaccine Adverse Event Reporting System (VAERS). The same procedure will be followed for the 2nd dose of the vaccine. Additionally, a detailed protocol has been developed by SYH for this intervention to handle adverse events, although none have occurred so far in the application of the COVID-19 vaccine to front line healthcare providers. Staff members have assigned specific responsibilities (e.g., if warranted, nurses will administer epinephrine or Benadryl and maintain an airway; outreach workers would call 911 and wait for the ambulance). The medical director of the study on behalf of SYH, [name] who is a licensed physician, will be on call at all times, and a licensed nurse will manage all aspects of the COVID-19 vaccination phase.

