14. POTENTIAL RISKS

Potential risks for study participation in the focus groups and survey include loss of confidentiality as a result of participating in this study. It is possible that participants may disclose confidential information about themselves. In order to provide participants with as much opportunity as possible to control access to information about themselves, recruitment and consent procedures will include thorough explanation of the purpose of the study, what participation entails, risks and benefits of participating in the study. Participants will also be told explicitly that participation is voluntary, consent can be withdrawn at any time during the study, and that there are no consequences for withdrawing from the study. Furthermore, a policies and procedures manual for the project will specify immediate data monitoring and response. Participants will be informed during the consent procedure that confidentiality may be breached under certain circumstances (i.e. they are a danger to themselves or others). In cases where a breach of confidentiality is necessary, project staff will be instructed to report to the project coordinator, who will file an incident report with [name] within 24 hours. The incident report requires a detailed account of the problem, date of occurrence, date it came to the PI's attention, impact on participant and corrective action taken. [name] will report adverse events to the UCSD IRB to make a determination if the event was related to research, directly or indirectly, and, if so, require revisions of protocol or consent, as applicable, and re-review of these procedures by the IRB with copies to the Office of Human Subjects for any necessary further action. Project staff hired through UCSD will be required to obtain ethical training through the CITI program (i.e., Social-Behavioral course) so that they are aware of the responsible conduct of research, and the types of adverse events that may warrant a breach of confidentiality. Monitoring of potential adverse effects or serious problems will be given high priority by project staff and researchers. All project staff will receive verbal and written instructions pertaining to the rules governing the maintenance of confidentiality upon completion of the study or if they leave the study before its completion. As previously mentioned, we are using an existing program to schedule participants follow-up appointments for the 2nd dose (NextGen) is currently being utilized by SYH because it is a safe and secure resource. NextGen sends automated reminders masking the direct line's outgoing and incoming phone numbers for text messaging and email reminders. Although there is no link between identity and the data (i.e., the unique code linking the surveys does not link to identifying information) this research is protected by the NIH Certificate of Confidentiality (CoC). The CoC will protect the privacy of research subjects by prohibiting disclosure of identifiable, sensitive research information to anyone not connected to the research.

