Any research involvement involves some risk of loss of confidentiality. Extensive measures will be taken to protect the confidentiality of the study participants and minimize any risk of a breach. All personal data collection will be conducted in private settings. Additionally, participants will be represented via a unique identifier for purposes of re-contact; contact/tracking information that include personal identifiers (i.e. first names, Google Voice number) will be linked with these unique identifiers on a list kept on a secured server in a password protected file, accessed only by the Research Coordinator and site Co-I at SYH. Only SYH research staff will have access to this list, and solely for identifying participants for scheduling their time for study participation. Clients unique IDs, and Google Voice number will be deleted immediately after completion of the data collection (i.e., after the 4-week follow-up). Audio-recordings from focus groups will be moved daily onto a secure UCSD server that is password-protected and backed-up daily and will be destroyed immediately after transcription is complete. Transcripts will not include personal identifiers and the document connecting personal identifying information to the list of unique survey identifiers will be destroyed as soon as data collection is completed. Additionally, research assistants and SYH clinical staff will be required to maintain confidentiality of all research participants and will be required to sign a pledge agreeing to do so upon joining the research project. They will not be permitted to report on anyone’s data or participation in this study.

All the FG participants will be asked to sign a written confidentiality agreement before participating in the session to ensure participants do not share with others outside the group what was discussed and by whom during the FG. Additionally,

during the FGs all participants will be requested to only refer to others using a pseudo name. Research assistants (RAs) will explain that confidentiality is critical to the safety and ability to share freely for all participants in the group. RAs will also remind participants that they may choose to not identify themselves or the experiences they share (for example, say that a friend had a particular experience even if it was their own experience). No identifiers will be recorded in transcripts.

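### The protocol places the follow-up survey both before and after the second dose at the mini-stations, and names no source that could give a series-completion rate (H.3, a primary outcome) in both arms

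*Protocol*

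**What the plan says.** **Order of events.** Protocol section 8, under Mini-vaccination stations, has participants who chose a two-shot vaccine "complete the follow-up survey (4-weeks) when they return for their second shot (during the observation period". Further on, the same subsection describes that visit again. It opens with "We will follow the same process as with the first dosage" and then says "they will complete the 5 min. survey, receive the 2nd shot of the COVID-19 vaccine, and pull aside for a 15-minute observation period". Under Phase II, section 8 says only that participants will be "asked to complete a 5 min survey during the follow-up visit", with no order. Section 12 describes survey then vaccine for the first visit and later adds "The same procedure will be followed for the 2nd dose of the vaccine".

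**Outcome.** Aim 1 states "H.3. more likely to complete vaccine series" as a hypothesis at follow-up. Section 8 (Data Analysis) and the SAP both make series completion one of two primary outcomes. Neither says how it is measured. Aim 2 compares completion between groups without naming a source. The survey block on vaccination history and uptake, given at baseline and at 4 weeks, is the only research capture of vaccination that is described.

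**Linkage.** Section 14 says "the unique code linking the surveys does not link to identifying information". Section 15 says a list does connect contact details to study IDs, but that staff may use it "solely for identifying participants for scheduling their time for study participation". Section 15 also has the IDs deleted once the 4-week follow-up is done, and its data and safety monitoring plan destroys linking data after the second-dose and follow-up survey collection.

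**The concern.** Staff at a mini-station cannot follow both descriptions. If they survey first, a participant asked about doses received answers minutes before the dose that completes the series. The stations are set up only at intervention sites, and no text fixes the order at the health centers or at the control sites. A recording error that falls mainly on one arm biases the comparison instead of merely adding noise to it.

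Behind this lies a wider gap. Completion needs a numerator and a denominator that includes people who never come back. A survey done on site at the second-dose visit reaches only those who do. Unless another source is named, and its use permitted while the ID link still exists, a primary outcome may not be recoverable in a form that compares the arms.

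**Working it through.** The documents state no figure for this point, so there is none to reproduce. The check sets the texts side by side, and a labelled illustration follows.

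**1. Same visit, two orders.** Both descriptions are in the mini-station text of section 8, both concern two-shot participants returning for dose 2, and both are current. In one the survey falls in the observation period; in the other it precedes the shot. They cannot both be followed.

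**2. What each order can record.** Take two-dose participants surveyed on site, with true return rate r.
- Survey before the shot: none can report the second dose, so reported completion among respondents is 0%.
- Survey after the shot: all have just had it, so reported completion is 100%.
- Non-returners have no on-site survey in either case.

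Neither 0% nor 100% depends on r. The on-site survey alone therefore cannot estimate completion in either order.

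**3. Feasibility of the after-dose order.** The follow-up survey is put at 5 minutes in section 8 and at 10 minutes in sections 9 and 12. Both fit the 15-minute observation period.

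**4. Illustration of an arm difference (all rates assumed).** Let u be uptake, t the share of vaccinated people choosing two doses, r the return rate, and b the share of returners surveyed before the shot. Suppose completion is taken from the survey, non-returners count as not complete, and nobody uses telephone or video follow-up. Then

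recorded completion = u(1 - t) + u·t·r·(1 - b), so the error is -u·t·r·b.

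Assume u = 0.60 and t = 0.70 in both arms, with r = 0.90 for 2VIDA! and 0.75 for control. Assume also that control sites survey after the dose (b = 0).
- Control: 0.18 + 0.42 × 0.75 = 0.495.
- 2VIDA!, b = 0: 0.18 + 0.42 × 0.90 = 0.558; difference +6.3 points (the true one).
- 2VIDA!, b = 1/6: 0.18 + 0.378 × 5/6 = 0.495; difference 0.
- 2VIDA!, b = 1/2: 0.18 + 0.189 = 0.369; difference -12.6 points.
- 2VIDA!, b = 1: 0.18; difference -31.5 points.

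The break-even share is b = 1 - 0.75/0.90 = 1/6. It does not depend on u or t; the size of the error is proportional to u × t. These figures show direction and sensitivity only.

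**5. Is another source available under the plan?** Clinic staff give the doses, schedule the second one in NextGen and notice missed appointments, so the information exists. But no text names it as the outcome source. Sections 14 and 15 disagree on whether a link exists, and section 15 limits the list to scheduling and then destroys it.

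**The case against.** The strongest reply is that the survey order hardly matters. The health centers hold the dose records, staff know who failed to attend, and completing the follow-up survey at the second-dose visit marks a return in either order. The questionnaire is not in the documents, so what a participant would actually be asked is unknown. Participants using telephone or video follow-up answer away from the dosing lane, possibly after dose 2.

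Much of this stands. A reader might infer that series completion cannot be recorded for anyone on a two-dose vaccine, or that both arms would record only one-shot recipients so that the comparison collapses to vaccine type. The documents do not support either reading. The explicit before-dose order covers only the intervention-arm mini-stations. The section 12 sentence "The same procedure will be followed for the 2nd dose of the vaccine" directly follows text on vaccination protocols and adverse-event reporting, so it may not refer to the survey at all. Telephone and video respondents are a further exception.

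What does not stand is the step from records existing to the outcome being secured. No text says that attendance or the clinic record defines completion, and the linkage rules as written work against using either.

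**Conclusion.** The point holds in a limited form. The two orders for the mini-station second-dose visit contradict each other, and the order at health centers and control sites is not set. Among two-dose participants surveyed on site, the before-dose order misses the dose given at that visit, and this could affect the intervention arm more than the control arm. The size cannot be derived from the documents; the illustration rests wholly on assumed rates and on survey-only capture.

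It would also go too far to infer that moving the survey repairs H.3. After the move, on-site respondents are all completers and non-returners are still missing. The larger defect is that a primary outcome has no stated source, time window or rule for non-returners, while the link needed to supply one is described inconsistently and is due to be destroyed. As written, the plan does not secure a sound completion rate in both arms. This should be settled while the ID list still exists.

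**What to change.** 1. Reconcile the two mini-station descriptions in section 8, and clarify its Phase II text and section 12, to a single order: follow-up survey after the dose, during the observation period, at all sites in both arms. This concerns data collection only and leaves the vaccination procedure unchanged.
2. Have health-center staff record dose number, vaccine type and date against the study ID at each vaccination in both arms. Name that record in the protocol and SAP as the source for H.2 and H.3, with a fixed time window. Count a participant on a two-dose series with no recorded second dose in the window as not complete. Returners and non-returners are then classified alike, wherever the survey falls.
3. Amend sections 14 and 15, including the data and safety monitoring plan, so that they agree that the link exists, allow this use, and keep the list until the dose fields are filled. Section 11 indicates that some participants have already finished both surveys, so their fields should be completed retrospectively where the link survives.

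**Cost.** Short protocol edits, three data fields filled by staff who already give and schedule the doses, and ethics-board wording for one extra use of the ID list. One limit remains: doses given outside the San Ysidro Health system would be known only by self-report.
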